4.4. Special notes on response assessment

When nodal disease is included in the sum of target lesions and the nodes decrease to 'normal' size (<10 mm), they may still have a measurement reported on scans. This measurement should be recorded even though the nodes are normal in order not to overstate progression should it be based on increase in size of the nodes. As noted earlier, this means that patients with CR may not have a total sum of 'zero' on the electronic case report form (eCRF).

In trials where confirmation of response is required, repeated ‘NE’ time point assessments may complicate best response determination. The analysis plan for the trial must address how missing data/assessments will be addressed in determination of response and progression. For example, in most trials it is reasonable to consider a patient with time point responses of PR-NE-PR as a confirmed response.

Patients with a global deterioration of health status requiring discontinuation of treatment without objective evidence of disease progression at that time should be reported as ‘symptomatic deterioration’. Every effort should be made to document objective progression even after discontinuation of treatment. Symptomatic deterioration is not a descriptor of an objective response: it is a reason for stopping study therapy. The objective response status of such patients is to be determined by evaluation of target and non-target disease as shown in Tables 1–3.

Conditions that define early progression, early death and inability to evaluate are study specific and should be clearly described in each protocol (depending on treatment duration, treatment periodicity).

In some circumstances it may be difficult to distinguish residual disease from normal tissue. When the evaluation of complete response depends upon this determination, it is recommended that the residual lesion be investigated (fine needle aspirate/biopsy) before assigning a status of complete response. FDG-PET may be used to upgrade a response to a CR in a manner similar to a biopsy in cases where a residual radiographic abnormality is thought to represent fibrosis or scarring. The use of FDG-PET in this circumstance should be prospectively described in the protocol and supported by disease specific medical literature for the indication. However, it must be acknowledged that both approaches may lead to false positive CR due to limitations of FDG-PET and biopsy resolution/sensitivity. For equivocal findings of progression (e.g. very small and uncertain new lesions; cystic changes or necrosis in existing lesions), treatment may continue until the next scheduled assessment. If at the next scheduled assessment, progression is confirmed, the date of progression should be the earlier date when progression was suspected.

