Nowadays it is accepted the important role of erlotinib in NSCLC tumors with EGFR mutations after at least one prior chemotherapy regimen (SATURN study)²¹. Therefore it is important to define the impact that treatment with erlotinib may have in the first line setting. There is some clinical trial evidence that EGFR TKIs are efficacious as first-line therapy in EGFR mutation positive patients with advanced NSCLC: IPASS is a phase III trial looking at gefitinib as a first-line treatment in non-small cell lung cancer in 1217 patients (261 EGFR mutation positive). Exploratory analysis of response rates in patients with EGFR mutations have shown a response rate of 71.2% in patients with EGFR mutations treated with gefitinib versus a response rate of 1.1% in patients without EGFR mutations treated with gefitinib²².

Therefore, erlotinib is currently being assessed as first-line treatment in advanced NSCLC in prospective, randomized, registration trials. There is however, already evidence that erlotinib works in first-line treatment with relevant results found for the evaluation of PFS. Paz-Ares²³ performed a pooled analysis of clinical outcomes in patients with EGFR mutations, treated with either an EGFR TKI or chemotherapy and demonstrated clinical efficacy of erlotinib (and gefitinib) monotherapy in 1st line NSCLC.

Table 1 - Summary of data included in pooled analysis

	Erlotinib	Gefitinib	Chemotherapy
Patients treated in any line, n	365	1069	375

Patients treated in first-line setting, %	57	57	95
---	----	----	----

Table 2 - Pooled analysis of outcomes according to line of therapy

	Pooled median PFS, months (95% accuracy interval)		
	Erlotinib	Gefitinib	Chemotherapy
Any line	13.2	9.8	5.9
	(12.0-14.7)	(9.2-10.4)	(5.3-6.5)
First-line	12.5	9.9	6.0
	(10.0-16.0)	(9.0-10.9)	(5.4-6.7)

The results of this pooled analysis are consistent with those from other studies looking at EGFR TKIs as first-line therapy in patients with EGFR mutations such as the IPASS study of first-line gefitinib versus carboplatin/paclitaxel in Asian patients with adenocarcinoma who were never- or light ex-smokers where the median PFS was found to be 9.5 months with gefitinib and 6.3 months with chemotherapy; and the Spanish Lung Cancer Group study of erlotinib in patients with EGFR mutations showed a medium PFS of 14.0 months and an ORR (complete and partial response) of 70.6%²⁴. These results highlight the idea that EGFR mutants lung cancer is a distinct class of NSCLC.

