8.2.6 Sample Size

The sample size was calculated based on the primary variable of the study, objective response rate. Since this proportion is unknown an exploratory sample size of 30 patients was considered to evaluate primary endpoint. This sample size will allow estimating ORR with a margin of error of approximately $\pm 17.5\%$, for a 95% confidence interval. Furthermore, approximately 2000 new cases of stage IIIB and IV NSCLC are diagnosed per year in Portugal¹ and, based on published data, expected prevalence of EGFR mutation is approximately 10%. With a 95% confidence interval, it was calculated that at least 420 patients will have to be enrolled to be tested to achieve 30 positive cases for the exploratory sample size analysis.

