3.5. New lesions

The appearance of new malignant lesions denotes disease progression; therefore, some comments on detection of new lesions are important. There are no specific criteria for the identification of new radiographic lesions; however, the finding of a new lesion should be unequivocal: i.e. not attributable to differences in scanning technique, change in imaging modality or findings thought to represent something other than tumour (for example, some ‘new’ bone lesions may be simply healing or flare of pre-existing lesions). This is particularly important when the patient’s baseline lesions show partial or complete response. For example, necrosis of a liver lesion may be reported on a CT scan report as a ‘new’ cystic lesion, which it is not.

A lesion identified on a follow-up study in an anatomical location that was not scanned at baseline is considered a new lesion and will indicate disease progression. An example of this is the patient who has visceral disease at baseline and while on study has a CT or MRI brain ordered which reveals metastases. The patient’s brain metastases are considered to be evidence of PD even if he/she did not have brain imaging at baseline. If a new lesion is equivocal, for example because of its small size, continued therapy and follow-up evaluation will clarify if it represents truly new disease. If repeat scans confirm there is definitely a new lesion, then progression should be declared using the date of the initial scan.

While FDG-PET response assessments need additional study, it is sometimes reasonable to incorporate the use of FDG-PET scanning to complement CT scanning in assessment of progression (particularly possible ‘new’ disease). New lesions on the basis of FDG-PET imaging can be identified according to the following algorithm:

a.) Negative FDG-PET at baseline, with a positive FDG-PET at follow-up is a sign of PD based on a new lesion.

b.) No FDG-PET at baseline and a positive FDG-PET at follow-up:

If the positive FDG-PET at follow-up corresponds to a new site of disease confirmed by CT, this is PD.

If the positive FDG-PET at follow-up is not confirmed as a new site of disease on CT, additional follow-up CT scans are needed to determine if there is truly progression occurring at that site (if so, the date of PD will be the date of the initial abnormal FDG-PET scan).

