#### 5.2.2 Per protocol (PP) population

Per protocol population will include all subjects enrolled in the treatment phase of the study without major protocol violations.

The protocol violations and corresponding impact are listed below.

Category	Impact
Assessment not performed	Minor/Major
Deviations from the dosing of the IPs	Major
Inconsistency with inclusion/exclusion criteria	Major
Non-compliance with the dose reduction schedule	Major
Prohibited concomitant medication	Major
Treatment not discontinued after withdrawal criteria is met	Major
Visit dates not per protocol	Minor

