### Treatment period

**Response duration:** It will be measured from the time of initial response (CR/PR whichever is first recorded) until documented tumor progression (in weeks).

**Best overall response:** a categorical variable will be obtained, defined as the best response across all time points, according to RECIST 1.1, until end of study treatment. The following criteria will be considered:

Complete response – Patients who presented at least one complete response;

Partial response – Patients who not presented a complete response and presented at least one partial response;

Stable disease – Patients who not presented response (complete or partial) and presented at least one stable disease;

Progression disease – Patients who not presented response or stable disease and presented progression disease;

Inevaluable – All assessments are inevaluable.

**Objective response:** A dichotomous variable (yes/no) will be calculated. Patients who presented complete response or partial response as the best overall response will be classified in “yes”. Otherwise patients will be classified in “no”.

**Event PFS:** A dichotomous variable (yes/no) will be calculated. Patients who presented progression disease or death for any cause will be classified in “yes”. Otherwise patients will be classified in “no”.

**Time PFS:** Time between baseline visit and date of first occurrence of disease progression or death for any cause (in weeks) while the patient was under study or during the prolonged follow-up period. In patients where disease progression or death from any cause was not observed, the time will be censored at the date of last visit or last contact with the patient.

**Time overall survival:** The time from the first dose of erlotinib (assumed to be baseline visit) to the date of death due to any cause (in weeks). For patients alive at the end of the follow-up period, the time was censored at the date of last visit or last contact with the patient.

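### Best overall response in SAP Appendix 3 is not cut off at the progression date, so a partial response recorded on or after a back-dated progression can count in the primary ORR

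*Protocol*

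**What the plan says.** **Dating of progression.** Protocol Appendix 1 deals with uncertain progression in two places. Section 4.4 lets treatment continue to the next scheduled assessment after an equivocal finding, and then says: "If at the next scheduled assessment, progression is confirmed, the date of progression should be the earlier date when progression was suspected". Section 3.5 has a matching rule for new lesions: "If repeat scans confirm there is definitely a new lesion, then progression should be declared using the date of the initial scan". SAP Appendix 5 reproduces both.

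**Best overall response.** SAP Appendix 3 (Treatment period) uses all time points to the end of study treatment and refers to RECIST 1.1. It then lists its own criteria. The partial response category is: "Patients who not presented a complete response and presented at least one partial response". Objective response is a yes/no variable built directly on this. Nothing there mentions the progression date, re-scoring of an earlier scan, or confirmation of response.

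**Time-to-event variables.** In the same appendix, PFS time runs from the baseline visit to the first progression or death. Response duration runs from the first recorded CR or PR to documented progression.

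**Confirmation.** Sections 4 and 4.6.1 of the RECIST text, in both documents, require CR and PR to be confirmed in a non-randomized trial with response as primary endpoint.

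**Size.** Protocol 8.2.6 states that "an exploratory sample size of 30 patients was considered to evaluate primary endpoint", with a "margin of error of approximately $\pm 17.5\%$, for a 95% confidence interval".

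**The concern.** The progression date is used in PFS and response duration but not in best overall response. The three variables can therefore contradict one another for the same patient: a responder in the ORR table whose progression is dated on or before the day of response.

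The error can only raise ORR. It affects the primary endpoint in both the ITT and the per-protocol tables. There is no independent review of scans (Protocol 8.1.3), so nothing downstream would correct the time-point score. A response duration of zero or less would also enter the Kaplan-Meier estimate with no stated handling.

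**Working it through.** **1. The plan's own precision figure.** Inputs: n = 30 and a 95% interval (Protocol 8.2.6). The normal-approximation half-width is 1.96 × √(p(1−p)/30).
- p = 0.60: 1.96 × √(0.24/30) = 0.175, or 17.5 points.
- p = 0.50: 1.96 × √(0.25/30) = 0.179, or 17.9 points.

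The stated figure reproduces, and this point does not change it.

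**2. Example patients under the literal rules.** Scans are every 8 weeks (Protocol 5.3). I assume that a scan with target PR and an equivocal lesion is entered as overall PR, because no definite new lesion is recorded. I also assume that PFS uses the back-dated progression, as SAP Appendix 5 directs.

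| Patient | Week 8 | Week 16 | Week 24 | PD date | SAP best response | Response duration |
|---|---|---|---|---|---|---|
| A | PR, equivocal new lesion | lesion confirmed | – | week 8 | PR | 8 − 8 = 0 weeks |
| B | PR, equivocal new lesion | PR, still equivocal | lesion confirmed | week 8 | PR | 8 − 8 = 0 weeks |
| C | SD, equivocal new lesion | PR, still equivocal | lesion confirmed | week 8 | PR | 8 − 16 = −8 weeks |

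B and C rest on section 3.5, which speaks of continued follow-up and repeat scans and does not limit these to one. All three patients are ORR responders with a PFS event at week 8. A patient whose first PR came before the back-dated PD date has a positive response duration and is not part of this problem.

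**3. Would confirmation alone solve it?** In A and C there is one PR followed by PD, which Table 3 of Appendix 1 classes as SD or PD, so confirmation removes them. In B the sequence is PR then PR. That meets a confirmation rule although both scans fall on or after the PD date. Only a cut-off at the PD date removes B.

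**4. Size.** Let k be the number of patients whose only PRs fall on or after the back-dated PD date. The documents do not give k, so I assume 0 to 3. Take 20 other responders, which puts the rate near the figure cited in Protocol 1.3 from a Spanish erlotinib study ("an ORR (complete and partial response) of 70.6"%). Intervals are exact (Clopper-Pearson); Protocol 8.2.1.1 specifies only the binomial distribution.

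| k | ORR, literal SAP rule | Exact 95% CI | ORR with cut-off |
|---|---|---|---|
| 0 | 20/30 = 66.7% | 47.2 to 82.7 | 66.7% |
| 1 | 21/30 = 70.0% | 50.6 to 85.3 | 66.7% |
| 2 | 22/30 = 73.3% | 54.1 to 87.7 | 66.7% |
| 3 | 23/30 = 76.7% | 57.7 to 90.1 | 66.7% |

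Each patient is worth 1/30 = 3.3 points.

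**The case against.** **The SAP invokes RECIST 1.1, which already settles it.** Table 1 of the RECIST text makes any new lesion overall PD. Section 4.3 determines best response once all the patient's data are known, and its table footnote shows an earlier score being changed in the light of later scans. A careful analyst could therefore re-score the early scan unprompted. This stands as a possible reading, so the miscount is not certain. But sections 3.5 and 4.4 move a date and do not say that the recorded time-point response changes. Where the text wants a score changed, as for a CR that should have been PR, it says so. The explicit SAP criteria are what a programmer will follow.

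**The real fault is the missing confirmation.** This is largely right for the simplest case: patient A would count as a responder even without back-dating, because one PR is enough. It is not the whole answer, as patient B shows.

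**The effect is small.** One patient is worth 3.3 points against a stated margin of about 17.5, and no hypothesis is tested (Protocol 8.2.2). That limits the importance of the point. It does not make a one-directional inconsistency in the primary endpoint acceptable.

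**A stronger reading to avoid.** Protocol Table 6 and SAP 5.2.2 list "Treatment not discontinued after withdrawal criteria is met" as Major. A reader might infer that treatment continued through an equivocal finding becomes a Major violation once progression is back-dated, so that confirmed progressors drop out of the per-protocol set and per-protocol PFS is inflated. The documents do not support this. The category mentions neither equivocal nor back-dated progression. Appendix 1 section 4.4 expressly permits the continuation. Protocol 4.6 does not name RECIST progression as a withdrawal criterion, and no passage applies the back-dated date to deviation status. Any per-protocol PFS shift would rest on that inference and on an invented frequency, and ITT is primary in any case.

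**Conclusion.** The point holds in a limited form. As written, SAP Appendix 3 can count as a response a PR recorded on or after the date that PFS treats as progression, and the response duration is then zero or negative. The size is 3.3 percentage points of ORR per affected patient, always upward. The number affected is unknown and may be zero.

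This rests on two assumptions: the equivocal scan is entered as PR, and the listed SAP criteria are applied literally and not overridden by the general reference to RECIST 1.1. It is a gap in a derivation rule that is cheap to close, not evidence that the reported ORR will be materially wrong. It supports no conclusion about the per-protocol set.

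**What to change.** In SAP Appendix 3, under best overall response, add two statements:
- Only assessments dated before the progression date used for PFS contribute to CR, PR or SD.
- Once progression is confirmed and dated back, the scan at that earlier date is re-scored as PD, so that a patient with no earlier assessment falls into the progressive disease category.

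The start of response duration then always precedes its end.

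Separately, reconcile the single-PR criterion in SAP Appendix 3 with the confirmation requirement in Protocol Appendix 1 and SAP Appendix 5. Neither change replaces the other. The sponsor may also wish to reconcile the Table 6 category on treatment not discontinued with the passages that allow continuation. Which of those governs is for the sponsor to decide.

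The cost is two sentences and deriving the progression date before best response. The downside is that ORR may be slightly lower.

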4.5. Frequency of tumour re-evaluation

Frequency of tumour re-evaluation while on treatment should be protocol specific and adapted to the type and schedule of treatment. However, in the context of phase II studies where the beneficial effect of therapy is not known, follow-up every 6–8 weeks (timed to coincide with the end of a cycle) is reasonable. Smaller or greater time intervals than these could be justified in specific regimens or circumstances. The protocol should specify which organ sites are to be evaluated at baseline (usually those most likely to be involved with metastatic disease for the tumour type under study) and how often evaluations are repeated. Normally, all target and non-target sites are evaluated at each assessment. In selected circumstances certain non-target organs may be evaluated less frequently. For example, bone scans may need to be repeated only when complete response is identified in target disease or when progression in bone is suspected.

After the end of the treatment, the need for repetitive tumour evaluations depends on whether the trial has as a goal the response rate or the time to an event (progression/death). If ‘time to an event’ (e.g. time to progression, disease-free survival and progression-free survival) is the main endpoint of the study, then routine scheduled re-evaluation of protocol specified sites of disease is warranted. In randomized comparative trials in particular, the scheduled assessments should be performed as identified on a calendar schedule (for example: every 6–8 weeks on treatment or every 3–4 months after treatment) and should not

be affected by delays in therapy, drug holidays or any other events that might lead to imbalance in a treatment arm in the timing of disease assessment.**.6. Confirmatory measurement/duration of response**

4.6.1. Confirmation

In non-randomized trials where response is the primary endpoint, confirmation of PR and CR is required to ensure responses identified are not the result of measurement error. This will also permit appropriate interpretation of results in the context of historical data where response has traditionally required confirmation in such trials. However, in all other circumstances, i.e. in randomized trials (phase II or III) or studies where stable disease or progression are the primary endpoints, confirmation of response is not required since it will not add value to the interpretation of trial results. However, elimination of the requirement for response confirmation may increase the importance of central review to protect against bias, in particular in studies which are not blinded.

In the case of SD, measurements must have met the SD criteria at least once after study entry at a minimum interval (in general not less than 6–8 weeks) that is defined in the study protocol.

4.6.2. Duration of overall response

The duration of overall response is measured from the time measurement criteria are first met for CR/PR (whichever is first recorded) until the first date that recurrent or progressive disease is objectively documented (taking as reference for progressive disease the smallest measurements recorded on study).

The duration of overall complete response is measured from the time measurement criteria are first met for CR until the first date that recurrent disease is objectively documented.

4.6.3. Duration of stable disease

Stable disease is measured from the start of the treatment (in randomized trials, from date of randomization) until the criteria for progression are met, taking as reference the smallest sum on study (if the baseline sum is the smallest, this is the reference for calculation of PD). The clinical relevance of the duration of stable disease varies in different studies and diseases. If the proportion of patients achieving stable disease for a minimum period of time is an endpoint of importance in a particular trial, the protocol should specify the minimal time interval required between two measurements for determination of stable disease.

19. Appendix 2: The ECOG Performance Scale

The Eastern Cooperative Oncology Group Performance Status Assessment
(Oken et al., 1982)

Grade	ECOG
0	Fully active, able to carry on all pre-disease performance without restriction.
1	Restricted in physically strenuous activity but ambulatory and able to carry out work of a light or sedentary nature, e.g., light house work, office work.
2	Ambulatory and capable of all self-care but unable to carry out any work activities. Up and about more than 50% of waking hours.
3	Capable of only limited self-care, confined to bed or chair more than 50% of waking hours.
4	Completely disabled. Cannot carry on any self-care. Totally confined to bed or chair.
5	Dead.

20. Appendix 3: Information on Potential Interactions

Erlotinib is metabolized in the liver by the hepatic cytochromes in humans, primarily CYP3A4 and to a lesser extent by CYP1A2, and the pulmonary isoform CYP1A1. Potential interactions may occur with drugs which are metabolized by, or are inhibitors or inducers of, these enzymes.

Potent inhibitors of CYP3A4 activity decrease erlotinib metabolism and increase erlotinib plasma concentrations. Inhibition of CYP3A4 metabolism by ketoconazole (200 mg p.o. BID for 5 days) resulted in increased exposure to erlotinib (86% in median erlotinib exposure (AUC)) and a 69% increase in C_{max} when compared to erlotinib alone. When erlotinib was co-administered with ciprofloxacin, an inhibitor of both CYP3A4 and CYP1A2, the erlotinib exposure (AUC) and maximum concentration (C_{max}) increased by 39% and 17%, respectively. Therefore caution should be used when administering erlotinib with potent CYP3A4 or combined CYP3A4/CYP1A2 inhibitors. In these situations, the dose of erlotinib should be reduced if toxicity is observed.

Potent inducers of CYP3A4 activity increase erlotinib metabolism and significantly decrease erlotinib plasma concentrations. Induction of CYP3A4 metabolism by rifampicin (600 mg p.o. QD for 7 days) resulted in a 69% decrease in the median erlotinib AUC, following a 150 mg dose of erlotinib as compared to erlotinib alone.

Pre-treatment and co-administration of rifampicin with a single 450 mg dose of erlotinib resulted in a mean erlotinib exposure (AUC) of 57.5% of that after a single 150 mg erlotinib dose in the absence of rifampicin treatment. Alternative treatments lacking potent CYP3A4 inducing activity should be considered when possible. For patients who require concomitant treatment with erlotinib and a potent CYP3A4 inducer such as rifampicin an increase in dose to 300 mg should be considered while their safety is closely monitored, and if well tolerated for more than 2 weeks, further increase to 450 mg could be considered with close safety monitoring. Higher doses have not been studied in this setting.

Pre-treatment or co-administration of erlotinib did not alter the clearance of the prototypical CYP3A4 substrates midazolam and erythromycin. Significant interactions with the clearance of other CYP3A4 substrates are therefore unlikely. Oral availability of midazolam did appear to decrease by up to 24%, which was however not attributed to effects on CYP3A4 activity.

The solubility of erlotinib is pH dependent. Erlotinib solubility decreases as pH increases. Drugs that alter the pH of the upper GI tract may alter the solubility of erlotinib and hence its bioavailability. Co-administration of erlotinib with omeprazole, a proton pump inhibitor, decreased the erlotinib exposure (AUC) and C_{max} by 46% and 61%, respectively. There was no change to T_{max} or half-life. Concomitant administration of erlotinib with 300 mg ranitidine, an H_2 -receptor antagonist, decreased erlotinib exposure (AUC) and C_{max} by 33% and 54%, respectively. Therefore, co-administration of drugs reducing gastric acid production with erlotinib should be avoided where possible. Increasing the dose of erlotinib when co-administered with such agents is not likely to compensate for this loss of exposure. However when erlotinib was dosed in a staggered manner, 2 hours before or 10 hours after ranitidine 150 mg b.i.d., erlotinib exposure (AUC) and C_{max} decreased only by 15% and 17%, respectively. If patients need to be treated with such drugs, then an H_2 -receptor

antagonist such as ranitidine should be considered and used in a staggered manner. Erlotinib must be taken at least 2 hours before or 10 hours after the H₂-receptor antagonist dosing. International Normalized Ratio (INR) elevations and bleeding events, including gastrointestinal bleeding, have been reported in clinical studies, some associated with concomitant warfarin administration. Coumarins (SintromTM; VarfarinTM) use is an exclusion criterion. If the patient requires anti-coagulation therapy, then the use of low molecular weight heparin instead of coumarins is recommended where clinically possible. In a phase Ib study, there were no significant effects of gemcitabine on the pharmacokinetics of erlotinib nor were there significant effects of erlotinib on the pharmacokinetics of gemcitabine (Core data sheet, 2009).

The following potent CYP3A4 inhibitors may *increase* erlotinib toxicity:

Systemic antifungals (e.g. ketoconazole, itraconazole, miconazole).

Erythromycin, clarithromycin, troleandomycin.

Selective serotonin reuptake inhibitors (e.g. nefazodone).

The following medications could decrease plasma levels of erlotinib and hence decrease efficacy, but they probably do not represent a safety concern:

- Antiepileptics (e.g. carbamazepine, phenobarbital, phenytoin).
- Rifampin, rifabutin.
- Troglitazone.
- Barbiturates.
- Glucocorticoids.
- Saint John's wort.

21. Appendix 4: 7th Edition AJCC Cancer Staging Manual - Part IV

Lung

(Carcinoid tumors are included. Sarcomas and other rare tumors are not included.)

At-A-Glance

SUMMARY OF CHANGES

- This staging system is now recommended for the classification of both non-small cell and small cell lung carcinomas and for carcinoid tumors of the lung
- The T classifications have been redefined:
 - T1 has been subclassified into T1a (≤ 2 cm in size) and T1b (>2 –3 cm in size)
 - T2 has been subclassified into T2a (>3 –5 cm in size) and T2b (>5 –7 cm in size)
 - T2 (>7 cm in size) has been reclassified as T3
 - Multiple tumor nodules in the same lobe have been reclassified from T4 to T3
 - Multiple tumor nodules in the same lung but a different lobe have been reclassified from M1 to T4
- No changes have been made to the N classification. However, a new international lymph node map defining the anatomical boundaries for lymph node stations has been developed
- The M classifications have been redefined:
 - M1 has been subdivided into M1a and M1b
 - Malignant pleural and pericardial effusions have been reclassified from T4 to M1a
 - Separate tumor nodules in the contralateral lung are considered M1a
 - M1b designates distant metastases

ANATOMIC STAGE/PROGNOSTIC GROUPS

Occult Carcinoma	TX	N0	M0
Stage 0	Tis	N0	M0
Stage IA	T1a	N0	M0
	T1b	N0	M0
Stage IB	T2a	N0	M0
Stage IIA	T2b	N0	M0
	T1a	N1	M0
	T1b	N1	M0
Stage IIB	T2a	N1	M0
	T2b	N1	M0
	T3	N0	M0

ICD-O-3 TOPOGRAPHY CODES

C34.0	Main bronchus
C34.1	Upper lobe, lung
C34.2	Middle lobe, lung
C34.3	Lower lobe, lung
C34.8	Overlapping lesion of lung
C34.9	Lung, NOS

“Used with the permission of the American Joint Committee on Cancer (AJCC), Chicago, Illinois. The original source for this material is the AJCC Cancer Staging Manual, Seventh Edition (2010) published by Springer Science and Business Media LLC, www.springer.com.”

ANATOMIC STAGE/PROGNOSTIC GROUPS (CONTINUED)			
Stage IIIA	T1a	N2	M0
	T1b	N2	M0
	T2a	N2	M0
	T2b	N2	M0
	T3	N1	M0
	T3	N2	M0
	T4	N0	M0
Stage IIIB	T4	N1	M0
	T1a	N3	M0
	T1b	N3	M0
	T2a	N3	M0
	T2b	N3	M0
	T3	N3	M0
	T4	N2	M0
Stage IV	T4	N3	M0
	Any T	Any N	M1a
	Any T	Any N	M1b

**ICD-O-3 HISTOLOGY
CODE RANGES**
8000–8576, 8940–8950,
8980–8981

INTRODUCTION

Lung cancer is among the most common malignancies in the Western world and is the leading cause of cancer deaths in both men and women. The primary etiology of lung cancer is exposure to tobacco smoke. Other less common factors, such as asbestos exposure, may contribute to the development of lung cancer. In recent years, the level of tobacco exposure, generally expressed as the number of cigarette pack-years of smoking, has been correlated with the biology and clinical behavior of this malignancy. Lung cancer is usually diagnosed at an advanced stage and consequently the overall 5-year survival for patients is approximately 15%. However, patients diagnosed when the primary tumor is resectable experience 5-year survivals ranging from 20 to 80%. Clinical and pathologic staging is critical to selecting patients appropriately for surgery and multimodality therapy.

ANATOMY

Primary Site. Carcinomas of the lung arise either from the alveolar lining cells of the pulmonary parenchyma or from the mucosa of the tracheobronchial tree. The trachea, which lies in the middle mediastinum, divides into the right and left main bronchi, which extend into the right and left lungs, respectively. The bronchi then subdivide into the lobar bronchi in the upper, middle, and lower lobes on the right and the upper and lower lobes on the left. The lungs are encased in membranes called the visceral pleura. The inside of the chest cavity is lined by a similar membrane called the parietal pleura. The potential space between these two membranes is the pleural space. The mediastinum contains structures in

between the lungs, including the heart, thymus, great vessels, lymph nodes, and esophagus.

The great vessels include:

- Aorta
- Superior vena cava
- Inferior vena cava
- Main pulmonary artery
- Intrapericardial segments of the trunk of the right and left pulmonary artery
- Intrapericardial segments of the superior and inferior right and left pulmonary veins

Regional Lymph Nodes. The regional lymph nodes extend from the supraclavicular region to the diaphragm. During the past three decades, two different lymph node maps have been used to describe the regional lymph nodes potentially involved by lung cancers. The first such map, proposed by Naruke (Figure 25.1) and officially endorsed by the Japan Lung Cancer Society, is used primarily in Japan. The second, the Mountain-Dresler modification of the American Thoracic Society (MD-ATS) lymph node map (Figure 25.2), is used in North America and Europe. The nomenclature for the anatomical locations of lymph nodes differs between these two maps especially with respect to nodes located in the paratracheal, tracheobronchial angle, and subcarinal areas. Recently, the International Association for the Study of Lung Cancer (IASLC) proposed a lymph node map (Figure 25.3) that reconciles the discrepancies between these two previous maps, considers other published proposals, and provides more detailed nomenclature for the anatomical boundaries of lymph nodes stations. Table 25.1 shows the definition for lymph node stations in all three maps. The IASLC lymph node map is now the recommended means

“Used with the permission of the American Joint Committee on Cancer (AJCC), Chicago, Illinois. The original source for this material is the AJCC Cancer Staging Manual, Seventh Edition (2010) published by Springer Science and Business Media LLC, www.springer.com.”

[figure not shown]

FIGURE 25.1. Naruke lymph node map. 1, Superior mediastinal or highest mediastinal; 2, paratracheal; 3, pretracheal; 3a, anterior mediastinal, 3p, retrotracheal or posterior mediastinal; 4, tracheo-bronchial; 5, subaortic or Botallo's; 6, paraaortic (ascending aorta); 7, subcarinal; 8, paraesophageal (below carina); 9, pulmonary ligament; 10, hilar; 11, interlobar; 12, lobar: upper lobe, middle lobe, and lower lobe; 13, segmental; 14, subsegmental. (From The Japan Lung Cancer Society. Classification of Lung Cancer. First English Edition. Tokyo: Kanehara & Co., 2000, used with permission.)

of describing regional lymph node involvement for lung cancers. Analyses of a large international lung cancer database suggest that for purposes of prognostic classification, it may be appropriate to amalgamate lymph node stations into "zones" (Figure 25.3). However, the use of lymph node "zones" for N staging remains investigational and needs to be confirmed by future prospective studies.

There are no evidence-based guidelines regarding the number of lymph nodes to be removed at surgery for adequate staging. However, adequate N staging is generally considered to include sampling or dissection of lymph nodes from stations 2R, 4R, 7, 10R, and 11R for right-sided tumors, and stations 5, 6, 7, 10 L, and 11 L for left-sided tumors. Station 9 lymph nodes should also be evaluated for lower lobe tumors. The more peripheral lymph nodes at stations 12–14 are usually evaluated by the pathologist in lobectomy or pneumonectomy specimens but may be separately removed when sublobar resections (e.g., segmentectomy) are performed. There is evidence to support the recommendation that histological examination of hilar and mediastinal lymph node specimen(s) will ordinarily include 6 or more lymph nodes/stations. Three of these nodes/stations should be mediastinal, including the sub-carinal nodes and three from N1 nodes/stations.

Distant Metastatic Sites. The most common metastatic sites are the brain, bones, adrenal glands, contralateral lung, liver, pericardium, kidneys, and subcutaneous tissues. However, virtually any organ can be a site of metastatic disease.

RULES FOR CLASSIFICATION

Lung cancers are broadly classified as either non-small cell (approximately 85% of tumors) or small cell carcinomas (15% of tumors). This general histological distinction reflects the clinical and biological behavior of these two tumor types. Approximately half of all non-small cell lung cancers (NSCLC) are either localized or locally advanced at the time of diagnosis and are treated by resection alone, or by combined modality therapy with or without resection. By contrast, small cell lung cancers (SCLC) are metastatic in 80% of cases at diagnosis. The 20% of SCLC that are initially localized to the hemithorax are usually locally advanced tumors managed by combination chemotherapy and radiotherapy. Less than 10% of SCLC are detected at a very early stage when they can be treated by resection and adjuvant chemotherapy.

The TNM staging system has traditionally been used for NSCLC. Although it is supposed to be applied also to SCLC, in practice these tumors have been classified as "limited" or "extensive" disease, a staging system introduced in the 1950s by the Veterans' Administration Lung Study Group for use in their clinical trials. Limited disease (LD) was characterized by tumors confined to one hemithorax, although local extension and ipsilateral supraclavicular nodes could also be present if they could be encompassed in the same radiation portal as the primary tumor. No extrathoracic metastases could be present. All other patients were classified as extensive disease (ED). In 1989, a consensus report from the IASLC recommended that LD be defined as tumors limited to one hemithorax with regional lymph node metastases including hilar, ipsilateral and contralateral mediastinal and ipsilateral and contralateral supraclavicular nodes. This report also recommends that patients with ipsilateral pleural effusion regardless of whether cytology positive or negative should be considered to have LD if no extrathoracic metastases were detected. More recently, analysis of an international database developed by the IASLC that includes 8088 SCLC patients showed that the TNM staging system is applicable to SCLC. Therefore, the staging system being presented in this edition of the staging manual should now be applied to both NSCLC and SCLC.

